Novavax's (NVX-CoV2373) protein based, novel but traditional immunizations have potential scientific advantages to the population through enhanced cross-reactivity which may facilitate activity against Coronavirus disease 2019 (COVID-19) variants.^{1,2} This technology also provides significant safety assurances to those wishing to utilize traditional immunization technology for their vaccination.³ There are two main challenges thought to largely explain the development of COVID-19 breakthrough infections: combination of variant mutations in the spike protein along with declines in antibodies.⁴

This randomized controlled trial (RCT) is comparing recipients of the 2023-2024 updated COVID-19 vaccines vs. non-recipients and Novavax (NVX) vs. mRNA 2023-2024 updated vaccines. The primary study hypothesis is to compare vaccine efficacy (VE) between participants who receive a 2023-2024 updated vaccine (mRNA or NVX) and participants who are recommended by the Advisory Committee on Immunization Practices (ACIP) to be vaccinated but decline the updated vaccine. The secondary hypothesis is to determine the relative vaccine efficacy (rVE) of the mRNA and the NVX 2023-2024 updated vaccines in preventing SARS-CoV-2 infection to confirm non-inferiority for NVX. This RCT may show evidence of the superiority of a blended vaccination approach of combining vaccines with different platforms.⁵

The trial will be conducted at the University of Utah (UT) Health for the upcoming SARS-CoV-2 virus circulation from Fall of 2023 to Spring of 2024. We aim to enroll 1500 participants who previously received at least two doses of the mRNA COVID-19 vaccine at least 90 days prior to enrollment. Upon enrollment, participants will be asked to describe their intention to receive a COVID-19 2023-2024 updated vaccines or not. Those who decide not to receive a vaccine during the study period will be placed in a non-randomized comparison group (n=300). Participants who intend to get vaccinated (n=1200) will be randomized into the NVX vaccine group or the mRNA vaccine group. Eligible participants will be randomized 1:1 to receive 1-dose of the NVX vaccine versus mRNA vaccine during November 2023 through February 2024. All eligible participants will be stratified by their age and sex within the respective groups.

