- Only the Investigator or delegated co-investigator or sub-investigator will make the decision to unblind the vaccine assignment.
- Only the affected participant will be unblinded.
- The designated study pharmacist(s)/designee at the study site will provide the unblinded vaccine assignment to the Investigator.
- The Investigator will notify the Novavax or Pfizer as soon as possible but no later than 24 hours after unblinding the participant.

Post Vaccination Safety Monitoring

- Per the Advisory Committee on Immunization Practices' General Best Practice Guidelines, all vaccine recipients will be observed for 15 minutes after vaccination for syncope. If the prevaccination survey reveals prior history of possible allergic reaction, the post-vaccination observation time-frame may be extended further to 30 minutes to further monitor for allergic reactions. Participants will be provided with contact information that can be utilized should they have any questions or adverse effects that arise after leaving the vaccination site. Additionally, 24 hours, 48 hours, and 6 days after receiving the vaccine, participants will be asked to complete a Post-Vaccination Survey (Appendix W) which will allow for monitoring events for 168 hours following vaccination.
- All study 2023-2024 updated COVID-19 vaccines have received EUA or approval from the FDA to be provided as a single dose, and data on reactogenicity events and adverse events will be documented. Study staff will provide participants with a phone number and email to call in case they have any questions after vaccination.
- Please note that due to changes in recommended language from the FDA, references to the
 vaccines in this protocol have been changed from "booster" to "2023-2024 updated COVID-19
 vaccines". However, we have maintained the booster reference in participant-facing
 documentation given that concept of a "booster" continues to be well recognized by the general
 public at this time, and much of the advertising for the study (including the study name itself)
 incorporates references to a booster.

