5.5.4 Follow-up Surveys

Brief surveys will be administered over the course of the study for three purposes. First, surveys will allow participants to update information on their occupation and work responsibilities, health status, potential exposures to COVID-19 at work, home, and in the community, and their use of PPE in these settings. Second, surveys will allow participants to report if they were unable to report a qualifying illness and/or submit illness specimens for any reason, and to provide an estimate of when this missed illness event occurred so that their surveillance record can be updated accordingly. Third, surveys will assess participants KAP regarding COVID-19 vaccines, intention to be vaccinated, and then after vaccination, to recall their overall health status on the days following vaccination.

- Post-Vaccination Survey (Appendix W. Post-Vaccination Survey), for participants who choose to receive a COVID-19 2023-2024 updated vaccine, will be administered 24 hours ±1 day, 48 hours ±1 day, and 6 days ±1 day after receiving the vaccine in order to monitor events for 168 hours following vaccination.
- Follow-up Survey 1 (Appendix O. Mid-Study Survey) will allow participants to report any adverse
 events following immunization (AEFI), and update chronic medical conditions, KAP responses,
 occupational, exposures, PPE use, and employer-mandated COVID-19 vaccination requirements.
 This survey will also give participants an opportunity to report their influenza vaccination status
 for the season. Participants also can report any illnesses missed during surveillance. All

- participants will be asked supplemental questions to collect information about receipt of COVID-19 vaccines outside of the study during the study period.
- Follow-up Survey 2 (Appendix O. End-of-Study Survey) will provide a final opportunity to allow participants to report any AEFI, and update chronic medical conditions, KAP responses, occupational, exposures, PPE use, and employer-mandated COVID-19 vaccination requirements. This survey will also give participants an opportunity to report their influenza vaccination status for the season. Participants also can report any illnesses missed during surveillance. All participants will be asked supplemental questions to collect information about receipt of COVID-19 vaccines outside of the study during the study period.

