 - o If participants indicate they want to withdraw from the study before completing the follow-up period, they will be invited to complete the End-of-Study Survey before withdrawal. Specific efforts will be made to collect survey responses from participants who did not complete the full follow-up period. The protocol status of all participants will be tracked in the database platform to record early termination, loss to follow-up, participant-directed withdrawal, and protocol completion. Utah study staff will complete the Participant Withdrawal Form (Appendix R5) for each participant who chooses to withdraw from the study.
- Long COVID Survey (Appendix P) will provide participants an opportunity to report Long COVID symptoms that last longer than 1 month. The survey will be distributed to participants with a first positive COVID-19 rapid test within the study (cases) and also participants who report their first COVID-like illness (CLI) symptoms during the study but did not test positive on the rapid test (controls). The survey will ask participants to identify which symptoms lasted more than 1 month, duration of these symptoms, and how these symptoms impact function and mental health. The Long COVID Survey will be distributed at the same time as the Mid-Study and End-of-Study Surveys.

Table 3. Survey Instruments and Timing

Instrument	Instrument Appendix Title Purpose		Purpose	Timing
Post- Vaccination Survey	W	Post- Vaccination Survey	To monitor for adverse events by answering questions about reactions to the vaccine for participants who choose to receive the COVID-19 2023-2024 updated vaccine	Day 1, Day 2, and Day 7 post- vaccination
Follow-up Survey 1	0	Mid-Study Survey	Self-reported documentation AEFI; update chronic medical conditions, KAP responses, occupational, exposures, PPE use, and employer-mandated COVID-19 vaccination requirements; report any illnesses missed during surveillance. They will be asked supplemental questions to collect information about receipt of COVID-	December 2023/January 2024

			19 vaccines outsides of the study during the study period.	
Follow-up Survey 2	0	End-of-Study Survey	Same as Mid-Study survey	April/May 2024

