9.1 Timeframe for Safety Assessments

The timing and frequency of all safety assessments are listed in Table 7.

Table 7. Timing and Frequency of all Safety Assessments

Study Period:	Screening Period	Clinic visit	Hours/Days after study vaccination		Months after study vaccination				
Study Day:	-30 to 0	0 ^a	24 hours	48 hours	6	28 days	3	6	EOSb
Study visit:	Screening	1	-	-	-		-	-	-
Randomization		Х							
Study vaccination ^c		Х							
Post-vaccination survey ^d (all vaccinated participants)		X	X	X	X				
Monitoring for COVID-19 ^e			COVID-19 surveillance will commence from Day 0 to up approximately 24 weeks after study vaccination ^e						
Unsolicited AEs that are study-related		Х	Х	X	X	Х	Х	Х	X
All unsolicited AEsf		Х	Х	Х	Х	Х			
SAEs/AESIs ^g	Х	Х	Х	Х	Х	Х	Х	Х	Х

^a The Screening visit and Day 0 visit may be combined if feasible.

Safety assessments will include monitoring and recording of solicited (local and systemic reactogenicity events) and unsolicited AEs, SAEs, and AESIs. UT is responsible for overseeing all IND submissions, which includes the capturing and reporting of these AEs, SAEs, and AESIs.

After study vaccination, participants will remain under observation at the clinic for at least 15 minutes for the presence of any acute reactions and solicited AEs. Solicited AEs, collected through the Post-

^b End of the study

^cStudy vaccination on Day 0 will consist of study vaccine only.

^d Solicited AEs (e.g., local and general systemic reactogenicity symptoms) will be captured in all participants on 24 hours, 48 hours, and 6 days after receipt of study vaccine. On study vaccination day, participants will remain in clinic for at least 15 minutes to be monitored for acute reactions and solicited AEs. Severe reactions will be noted as AEs on day of study vaccination.

^e Participants will monitor for COVID-19 symptoms weekly during the surveillance period. Participants will self-collect rapid antigen tests on a weekly basis to monitor for COVID-19 during the surveillance period. Illnesses that occur more than 28 days after administration of the study vaccine will not be reported as AEs unless a study investigator determines that the illness is related to the study vaccine.

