^f All unsolicited AEs may be reported to the study team from the time of study vaccination completion to the participant's last study-related procedure. Unsolicited reports that occur more than 28 days after administration of the study vaccine will not be reported as AEs unless a study investigator determines that the illness is related to the study vaccine.

^g SAEs/AESIs may be reported to the study team from the time of study vaccination completion to the participant's last study-related procedure, which is approximately 24 weeks after study vaccination.

Vaccination Survey (Appendix W), will be recorded 24 hours, 48 hours, and 6 days after study vaccination in all participants.

All solicited AEs captured within 7 days of vaccination will be recorded on the University of Utah Adverse Event (AE) Log (Appendix R2).

All unsolicited AEs captured within 28 days of vaccination will be recorded on the University of Utah Adverse Event (AE) Log (Appendix R2). Medical events that begin prior to study vaccination will be recorded as medical history on the Enrollment Survey (Appendix F) and not the University of Utah AE Log.

All unsolicited AEs of any severity may be reported to the study team from the time of study vaccination completion to the participant's last study-related procedure. Unsolicited reports that occur more than 28 days after administration of the study vaccine will not be reported as AEs unless a study investigator determines that the illness is related to the study vaccine.

All SAEs may be reported to the study team from the signing of informed consent until completion of the participant's last study-related procedure. Study staff will record all SAEs on the University of Utah Serious Adverse Event (SAE) Log (Appendix R3).

All AEs will be followed until resolution or withdrawal from the study. All AEs, SAEs, and AESIs will be followed until resolution, until the end of the study, until clinically stable or considered chronic, or withdrawal from the study. In the case of persistent non-response from a participant reporting an AE, SAE, or AESI, staff will make at least three attempts to contact the participant via differing methods (text message, phone call, email) over 30 days. At which point, the event will be reported with all available information and administratively closed.

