Medical judgment should be exercised in deciding whether SAE reporting is appropriate in other situations, such as important medical events that may not be immediately life-threatening or result in death or hospitalization but may jeopardize the participant or require medical or surgical intervention to prevent one of the other outcomes listed in the above definition. These events should usually be considered serious. Examples of such medical events include allergic bronchospasm requiring intensive treatment in an emergency room or at home, blood dyscrasias or convulsions that do not result in inpatient hospitalization, or the development of drug dependency or drug abuse.

Adverse Events of Special Interest (AESI)

Myocarditis and pericarditis are our AEs of special interest. All AESIs may be reported to the study team from the time of study vaccination to the participant's last study-related procedure. AESIs will be captured through participant report only.

Myocarditis and Pericarditis

Due to the risk of myocarditis and pericarditis with the COVID-19 vaccines, participants reporting signs and symptoms of acute chest pain, shortness of breath, palpitation, or other signs or symptoms of myocarditis and pericarditis within 4-6 weeks after vaccination will be referred to a cardiologist for evaluation and management. Cases of myocarditis and pericarditis will be followed until resolution of symptoms and abnormal test findings.

At the study visit, vaccinated participants will receive an informational sheet (Appendix V5. Myocarditis and Pericarditis Information Sheet) describing the signs and symptoms of myocarditis and pericarditis

and guidance on seeking medical care and contacting study personnel. Participants reporting signs and symptoms of myocarditis or pericarditis may notify the study staff at any time via any and all methods of communication (i.e. email or phone call or text message).

In the event a participant report signs and symptoms or diagnoses of myocarditis and pericarditis, the Investigator will refer to the CDC case definitions for myocarditis, pericarditis, and myopericarditis (https://www.cdc.gov/mmwr/volumes/70/wr/mm7027e2.htm) when making the determination.

In terms of reporting, cases of myocarditis or pericarditis occurring in temporal association with vaccination will be considered a potentially related, unexpected, and serious reaction (SUSAR) and will require expedited reporting to the FDA.

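### The last post-vaccination survey does not assure the 168 hours claimed, and the calendar-dated Mid-Study Survey comes before every February dose

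*Protocol*

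**What the plan says.** **Reactogenicity surveys.** Protocol section 5.5.4 gives the times as "24 hours ±1 day, 48 hours ±1 day, and 6 days ±1 day after receiving the vaccine in order to monitor events for 168 hours". Section 5.5.3 repeats the schedule without a tolerance: "24 hours, 48 hours, and 6 days after receiving the vaccine". The footnote to Table 7 in section 9.1 says solicited events "will be captured in all participants on 24 hours, 48 hours, and 6 days after receipt of study vaccine". Table 3 (section 5.5.4) instead lists "Day 1, Day 2, and Day 7 post- vaccination", and Table 6 (section 8.6) pays for a Day 7 survey. Sections 9.1 and 9.2 set a 7-day window for solicited events. After that only unsolicited events are reported.

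**Later windows.** Section 9.1: "All unsolicited AEs captured within 28 days of vaccination will be recorded". Section 9.2 says participants will be assessed for unsolicited events to Day 28 and sets a Day 35 limit for medically attended events. For events of special interest, "AESIs will be captured through participant report only". Participants with symptoms suggesting myocarditis or pericarditis "within 4-6 weeks after vaccination will be referred to a cardiologist for evaluation and management".

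**Instruments after the first week.** Section 5.5.4 names two surveys that ask about adverse events following immunisation. Table 3 dates Mid-Study to December 2023/January 2024 and End-of-Study to April/May 2024. The protocol's opening summary has vaccine given "during November 2023 through February 2024". Table 7 marks assessments at 28 days, 3 months and 6 months, shows no visit at those points and names no instrument. Appendix Q places the End-of-Study Survey in a column headed Sep-Oct 2024.

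**The concern.** A safety window is only as good as the question that closes it. Two things look wrong here. The last solicited-reaction survey has two different times, and the time used in most of the text need not reach the end of the period it is said to cover. The next two adverse-event surveys are tied to calendar months, while each participant's windows run from the day of the dose.

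If Table 3 is followed, how well an event inside 28 days is captured depends on when the person was vaccinated. Early vaccinees can be asked soon after the window closes. Late vaccinees are asked weeks or months afterwards, or must volunteer the event. Section 9.2 says the adverse-event capture described there reflects what was required under the IND, so an undelivered window matters even though safety is not a listed objective.

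**Working it through.** **Step 1: hours covered by the last post-vaccination survey.** The input is 6 days ±1 day (section 5.5.4) against a stated 168 hours.

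- Stated figure: 7 × 24 = 168 h. It is reproduced by Day 7 in Tables 3 and 6 (taking Day 1 as 24 h) and by the upper edge of the ±1 day window.
- Nominal time: 6 × 24 = 144 h, so 168 − 144 = 24 h short (24/168 = 14%).
- Lower edge: 5 × 24 = 120 h, so 168 − 120 = 48 h short (48/168 = 29%).

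**Step 2: Mid-Study Survey against dosing dates.** Inputs: dosing from 1 November 2023 to 29 February 2024, and the survey in December or January (Table 3). The date most favourable to the plan is 31 January 2024.

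- A 1 February dose comes 1 day after that survey, and a 29 February dose 29 days after. Every February dose is therefore missed.
- 31 January − 28 days = 3 January. Doses after 3 January have not completed 28 days.
- 31 January − 35 days = 27 December. Doses after 27 December have not completed 35 days.

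**Step 3: share affected.** The documents give no accrual curve, so uniform dosing is an assumption. The dosing period is 30 + 31 + 31 + 29 = 121 days.

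| Survey date | Dosed after the survey | Day 28 not reached by the survey |
|---|---|---|
| 31 January (latest) | 29/121 = 24%, about 288 of 1,200 | (28 + 29)/121 = 57/121 = 47%, about 565 of 1,200 |
| 1 December (earliest) | (30 + 31 + 29)/121 = 90/121 = 74% | (121 − 3)/121 = 118/121 = 98% |

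The last cell uses 1 December − 28 days = 3 November. The February share moves directly with accrual: 10% of doses in February would be 120 people and 40% would be 480.

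**Step 4: next named adverse-event survey for February doses.** This is End-of-Study, 1 April to 31 May 2024 by Table 3.

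- 1 February dose: day 60 to day 120.
- 29 February dose: day 32 to day 92.
- Day 28 for these doses falls between 29 February and 28 March, always before that survey.

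No named adverse-event questionnaire therefore falls between about day 7 and day 32 to 120 for these participants.

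**Step 5: End-of-Study timing.** Follow-up is 24 weeks = 168 days (section 5.2). 31 May 2024 − 168 days = 15 December 2023, so for doses after 15 December the Table 3 survey comes before follow-up ends. A 29 February dose reaches 24 weeks on 15 August 2024. Appendix Q's Sep-Oct 2024 would be after that date. The two entries cannot both be right.

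**Step 6: weekly contact and the myocarditis text, side by side.** The weekly symptom list in section 5.5.2 includes shortness of breath but not chest pain or palpitations. A positive answer leads to a detailed symptom checklist (Appendix H) and, if symptoms are ongoing, to antigen testing. Section 9.2 names all three symptoms as grounds for referral. The protocol does not say how the weekly contact connects to that text.

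**The case against.** The case against a stronger reading is substantial, and much of it stands.

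- A reader might infer that the surveys cannot reach 168 hours. They can: the upper edge of the window and the Day 7 entries in Tables 3 and 6 both do. The defect is an inconsistency and a lack of assurance.
- A reader might infer that late solicited reactions are never asked about. Appendix Q puts the first weekly contact at study day 7 (window 6 to 9 days). Its list of illness symptoms (section 5.5.2) covers the general systemic reactions named in section 8.7. Section 9.2 adds investigator assessment of overlapping symptoms in the first 7 days. Late local reactions are the part without an evident prompt.
- A reader might infer that February vaccinees face no adverse-event question at all before April. The Post-Vaccination Survey is such a question, so the gap begins at about day 7.
- A reader might infer that nothing asks about adverse events at 28 days, 3 months or 6 months. The documents support only that no instrument is named. Section 5.5.2 mentions one to four further weekly questions of unstated content, and Appendices G1, H, O, W and S2 are not available to check. The SAP (section 9) refers reactogenicity to a separate substudy plan.
- A reader might infer that safety rates are understated or the vaccine comparison biased. End-of-Study recall and spontaneous reports still reach these events, and section 9.2 provides an information sheet and open reporting channels. Randomisation in blocks of six within strata (section 5.5.3) keeps the two vaccines closely balanced over calendar time.

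None of this changes Table 3's dates or removes the conflict between 6 days and Day 7.

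**Conclusion.** The point holds in a limited form.

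1. The last Post-Vaccination Survey has two stated times, and the ±1 day version spans 120 to 168 hours, so the 168-hour solicited window is not assured. The shortfall is 24 hours at the nominal time and 48 hours at the early edge.
2. By Table 3, the Mid-Study Survey precedes every February dose and precedes Day 28 for doses after 3 January. On the survey's latest date and with uniform dosing, that is about 24% and 47% of vaccinees. The calendar conflict itself needs no accrual assumption; only the percentages do.
3. For February doses the 28-day unsolicited window rests on recall at day 32 to 120 and on spontaneous reports, unless the unseen appendices supply a question. The day range depends on Table 3's April/May date, which Appendix Q contradicts.

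The consequence is uneven safety ascertainment by dosing date. A loss of events is plausible but cannot be quantified from the documents. The efficacy analyses and the NVX versus mRNA contrast are little affected. The change should be made because the stated windows are not tied to instruments that deliver them.

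**What to change.** (a) Give the third Post-Vaccination Survey one consistent time in sections 5.5.3, 5.5.4 and 9.1 and in Tables 3 and 6. Set its window so that a completed survey cannot end the observed period before 168 hours, and have it ask about the whole period since the previous survey.

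(b) In Table 3, trigger the Mid-Study and End-of-Study Surveys by days since vaccination (or enrolment, for the comparison group) rather than by calendar month. Every vaccinee should have an adverse-event question after the 28-day window closes, and End-of-Study should fall at the end of 24 weeks. Name the instrument behind each Table 7 mark, and bring Appendix Q into line. If the appendices already contain such questions, say so in Tables 3 and 7.

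(c) Reconcile the myocarditis and pericarditis symptom text in section 9.2 with the weekly symptom list and routing in section 5.5.2. Which clinical rule should apply is for the investigators and is not proposed here.

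The cost is changed trigger dates in an existing portal, a short amendment and slightly more adverse-event reports to review.

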4.2 Secondary Objectives

- 1. Evaluate the effect of prior number of doses of COVID-19 vaccination during the preceding 3 years on the relative efficacy of a single dose of NVX.
- 2. Assess the vaccine efficacy against asymptomatic or any (asymptomatic or symptomatic) RAT-confirmed SARS-CoV-2 infections.
- 3. Examine the individual, occupational, and environmental predictors of SARS-CoV-2 infection and compare these predictors between asymptomatic infection versus symptomatic COVID-19 illness.
- Describe the clinical characteristics and outcomes associated with COVID-19.³⁷
 - a. Determine the duration and severity of illness and examine the socio-demographic and health characteristics associated with prolonged or severe illness.
 - b. Determine the impact of COVID-19 on indicators of functioning, including missed work, ability to complete normal work and home activities, and working while ill.
 - c. Determine the proportion of COVID-19 illnesses that are medically attended and examine the factors associated with seeking medical care and treatment.
- 5. Compare illness characteristics and duration with primary vs. re-infection with SARS-CoV-2 during the study window.
- 6. Examine if VE is modified by socio-demographic characteristics, occupation, health status, or other risk factors.
- 7. Examine if 2023-2024 formula (monovalent, Omicron XBB.1.5 containing) vaccines modifies illness severity and duration among participants with breakthrough infection despite vaccination.
- 8. Assess the incidence of post-COVID conditions (PCC) and factors associated with PCC symptoms.
- Determine if PCC symptoms differ among vaccinated and participants who decline the 2023-2024 updated vaccine.
- 10. Determine if PCC symptoms are modified by vaccination status (e.g. 2-, 3-, and 4+ doses) prior to infection.
- 11. Characterize the knowledge, attitudes, and practices (KAPs) of participants related to new COVID-19 2023 vaccine variant vaccines and examine the associations between KAP and subsequent vaccination behaviors (including vaccine refusal, hesitancy, or incomplete adherence to vaccination recommendations).

5. Methods

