Study Duration: Study activities will commence following Institutional Review Board (IRB) approval. We aim to begin recruitment activities, i.e., identifying and screening potential participants, in November 2023. We anticipate initiating enrollment in November 2023 and start data collection immediately after enrollment. The vaccine campaign is estimated to begin in November 2023 and end in February 2023. All participants will start active surveillance immediately following their enrollment visit. Participants will complete all surveillance activities for a total of 24 weeks from the date of enrollment/vaccination. Surveillance activities are estimated to end Summer 2024. Close-out activities will begin in September 2024.

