Long COVID Survey	Р	Long COVID Survey	The intended recipients are participants who had an illness that lasted longer than 4 weeks. The survey asks about symptoms that lasted at least 4 weeks, how long each symptom lasted, and how bothersome the symptoms were. The survey also asks questions about mental health of the participant.	Distributed to all cases and controls at the same time as the Mid-Study and End-of- Study surveys.

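### The protocol gives three conflicting timings for the final Long COVID survey, and the Table 3 date (April/May 2024) is too early for participants enrolled up to February 2024 and followed for 24 weeks

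*Protocol*

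**What the plan says.** Secondary objective 8 (protocol section 4.2) is: "Assess the incidence of post-COVID conditions (PCC) and factors associated with PCC symptoms". Objectives 9 and 10 compare post-COVID conditions (PCC) by receipt of the updated vaccine and by prior doses.

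The dedicated instrument is the Long COVID Survey. Table 3 describes its content: "The survey asks about symptoms that lasted at least 4 weeks, how long each symptom lasted, and how bothersome the symptoms were". Section 5.5.4 ties its dispatch to two other surveys: "The Long COVID Survey will be distributed at the same time as the Mid-Study and End-of-Study Surveys". Table 3 dates these "December 2023/January 2024" (Mid-Study) and "April/May 2024" (End-of-Study).

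The opening summary gives the enrolment window: "Eligible participants will be randomized 1:1 to receive 1-dose of the NVX vaccine versus mRNA vaccine during November 2023 through February 2024". Section 5.2 gives the follow-up: "Participants will complete all surveillance activities for a total of 24 weeks from the date of enrollment/vaccination".

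Two other places time the End-of-Study survey differently:
- Appendix Q has a schedule running to week 26, day 182 (window 180-190). It marks the End-of-Study survey, and a Long COVID survey, under Study End in September-October 2024.
- Section 5.5.3 (Blinding) defines completion of data collection as following the End Study Survey and expects unblinding in June-July 2024.

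No text says which timing governs, and no Long COVID survey is timed from illness onset.

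**The concern.** A survey that asks about symptoms lasting 4 weeks or more can only classify an infection that began at least 4 weeks before it is completed. An infection that is too recent at the Mid-Study survey can still be picked up at the End-of-Study survey, so the date of the last survey decides what is lost. Table 3 fixes that date in April or May for everyone, while late enrollees remain under surveillance into August. Section 5.5.4 and Table 3 are where staff would look to programme the portal.

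At stake is the set of infections that objectives 8-10 can use. If Table 3 is followed, whether an infection can be assessed depends on when the participant enrolled. The SAP gives no minimum interval from onset to survey, and SAP section 7.2 makes no adjustment for missing values.

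**Working it through.** The documents give no figure for survey coverage, so there is none to reproduce. The check is date arithmetic.

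**Inputs from the documents.** Enrolment November 2023 to February 2024, taken as 1 November to 29 February (121 days); 24 weeks = 168 days of surveillance each; 4 weeks = 28 days of symptoms; last survey in April/May 2024 (Table 3), day 180-190 or September-October 2024 (Appendix Q), or before unblinding in June-July 2024 (section 5.5.3).

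**Assumptions, not in the documents.** Uniform enrolment and constant hazard, both varied below.

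**End of surveillance.** 1 November 2023 + 168 days = 17 April 2024. 29 February 2024 + 168 days = 15 August 2024. With uniform enrolment, 76 of 121 enrolment days (63%) lead to surveillance beyond 31 May. February supplies 29 of 121 (24%), after Table 3's Mid-Study date.

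**Formula.** For enrolment day *e* and follow-up day *d* = 0 to 167, an infection at *t* = *e* + *d* is never surveyed if *t* > S, and surveyed too early if 0 ≤ S − *t* < 28, where S is the last survey date. Shares are of 121 × 168 = 20,328 person-days.

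| Last survey S | Too early | Never | Not assessable |
|---|---|---|---|
| 1 April | 3,388 (16.7%) | 9,075 (44.6%) | 61.3% |
| 30 April | 3,283 (16.2%) | 5,671 (27.9%) | 44.0% |
| 31 May | 2,506 (12.3%) | 2,850 (14.0%) | 26.3% |
| 30 June | 1,666 (8.2%) | 1,035 (5.1%) | 13.3% |
| 31 July | 798 (3.9%) | 105 (0.5%) | 4.4% |
| 1 September | 55 (0.3%) | 0 | 0.3% |

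**By enrolment date, 30 April survey.** For a 1 November enrollee S is day 181, so days 154-167 are too recent: 14/168 = 8.3% not assessable. For a 29 February enrollee S is day 61, so only days 0-33 qualify: 34/168 = 20.2% assessable.

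**Appendix Q read as participant time.** No infection is missed altogether. Days surveyed too early: survey at day 180, 15/168 = 8.9%; day 182, 13/168 = 7.7%; day 190, 5/168 = 3.0%. At day 196 (168 + 28) the share is 0.

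**Sensitivity with Table 3 dates (1 April to 31 May).** All enrolment in November: 34.2% to 1.5%. All in February: 88.7% to 53.0%. Winter-weighted hazard, assumed to halve every 6 weeks after 31 January: 32.2%, 16.6% and 6.8% for 1 April, 30 April and 31 May.

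**The case against.** The strongest reply is that Table 3 may simply be out of date. Under Appendix Q no infection goes unsurveyed, and at most about 9% are surveyed too early; under a June-July survey the share is about 13% (30 June) to 4% (31 July). This stands. A reader might infer that a quarter to three-fifths of infections will be lost. The documents do not support that as a prediction, because it requires Table 3 to govern. The constant hazard also sits poorly with the wintertime circulation the protocol anticipates.

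Four other stronger readings should be set aside:
- **That PCC is captured only by this survey.** Section 5.1 mentions PCC symptom reporting at enrolment, mid-study and end of study, and section 5.5.2 follows ill participants weekly until at least 90% recovery. These record some prolonged illness, but the weekly messages stop with surveillance and are not described as a substitute for the survey's content.
- **That the loss biases the vaccinee-decliner comparison.** This would need enrolment dates to differ by group. Section 5.4 only lists actions to take if decliner recruitment lags, and section 5.5.3 has both groups self-scheduling or walking in at the same sites.
- **That infections too recent to assess would be counted as PCC-free.** No text says so. Onset dates are collected, so they can be excluded.
- **That the denominator is lost through the recipient wording.** Table 3 does say "The intended recipients are participants who had an illness that lasted longer than 4 weeks". But its timing cell covers all cases and controls, section 5.5.4 defines those groups without a duration condition, and Table 6 pays on the same basis. This is a wording slip.

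**Conclusion.** The protocol contradicts itself on when the End-of-Study survey and its accompanying Long COVID survey are sent, and the Table 3 date cannot be right for this enrolment window and follow-up. If Table 3 is followed, about 26-61% of infections are not assessable under uniform enrolment and constant hazard, or about 7-32% with the assumed winter weighting. Under the later timings the share runs from 0.3% to about 13%. The actual figure depends on enrolment pace and epidemic timing, which the documents do not give. The mismatch itself does not depend on those assumptions.

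The effect is confined to secondary objectives 8-10; neither primary analysis is touched. The point should be corrected because following the stated date would remove usable outcome data and the remedy is cheap.

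**What to change.** 1. Replace the Table 3 calendar dates for the final survey with participant time: send the final Long COVID survey to every case and every RAT-negative CLI control at least 28 days after the participant's week-24 contact (day 196 or later). For a 29 February enrollee that is 12 September 2024, within Appendix Q's September-October study end.
2. Align Table 3, Appendix Q and the Blinding text in section 5.5.3 with that rule.
3. State in the SAP that the PCC denominator is limited to infections with at least 28 days from onset to survey.
4. Reword the Table 3 recipient sentence to match its all-cases-and-controls cell.

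**Cost.** Portal scheduling and text edits, with no new instrument or visit. The last online contact moves later, to mid-September for the last enrollees. Two places must then be reconciled with it: the June-July unblinding, which section 5.5.3 ties to the end of data collection, and the footnote to Table 7 (section 9.1) that puts the last study-related procedure, and so the end of SAE/AESI reporting, at about 24 weeks after vaccination. The unblinding date needs attention in any case: 14 February + 168 days = 31 July, so anyone enrolled after 14 February is still under surveillance when July ends.
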